
Target sample size:
	
Since there is no study that has explored the prevalence of IBS during a fertility treatment, there is not enough data to do a power analysis before starting this study. This study will be an explorative study with a PCOS group of 60 and social freezing group of 60. After the data has been collected, a power analysis will be done and the option of including more participants will be explored. In this case, we will submit an amendment to the ethical committee.
 
There are multiple studies that found a connection between IBS and infertility. Most of these studies are retrospective studies and are focused on male infertility. (1). A study in 2013 analyzed gastro-intestinal symptoms during IVF in infertile women. This study had 124 participants. (2) Since this study from 2013 is the most like our study, the aim for our target sample size is going to be similar, namely 120 participants.

5 Background and Rationale

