5.6 IBS prevalence

The Rome Foundation Global study reported an overall prevalence of 3,8% when the Rome IV criteria are used and an overall prevalence of 10,1% when the Rome III criteria are used. (15) The Rome IV criteria question the prevalence of abdominal pain while the Rome III criteria additionally ask for abdominal discomfort (an uncomfortable sensation and not necessary pain). (16) Women have a significant higher prevalence of IBS than men, up to 3-fold higher. The risk of IBS doubles

when the person has a biological relative with IBS. The prevalence of IBS varies greatly between different countries. (17) PCOS patients are more prone to experience gastrointestinal (GI) disturbances such as irritable bowel syndrome (IBS): a recent meta-analysis showed that the risk of IBS in women with PCOS is two times higher than in a control group of women with no PCOS. (18) The prevalence of IBS during a fertility treatment has not been studied.

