10.5 Statistical Considerations and Data Analysis

The primary objective of this study is to investigate whether fertility treatment is associated with changes in the **prevalence** and **severity** of Irritable Bowel Syndrome (IBS) symptoms. Specifically, the study aims to:

3. Assess whether the **proportion of participants meeting IBS diagnostic criteria** (based on ROME III and IV) differs **before and after fertility treatment**.
4. Evaluate whether there is a **statistically significant change in IBS symptom severity** as measured by the **IBS Symptom Severity Score (IBS-SSS)** before and after treatment.
5. Identify which **psychological and clinical factors** are associated with the presence or change in IBS symptoms in women undergoing fertility treatments, including those with **Polycystic Ovary Syndrome (PCOS)** and those undergoing **social oocyte freezing**.

Participants will either meet the criteria for IBS or not meet the criteria for IBS (based on the ROME III and IV criteria). This will correlate to a binary outcome: yes (1) or no (0) answer. This answer will be defined before and after the fertility treatment. A logistic regression model will be used to determine the chance of P(1) which is the chance of meeting the IBS criteria (yes answer). This regression model will be used for the PCOS group and the social freezing group. This model estimates the probability of an event occurring (meeting the IBS criteria) based on a given set of independent variables. The independent variables include GAD-7 score, PHQ-9 score, ethnicity, duration of the desire to have children, the number of follicles found on the US,...

These independent variables will be evaluated with the AIC (Akaike information criterion). AIC is used to compare different possible regression models and define which model is the best fit for the given data. If the AIC is lower, the data is a better fit. The regression model will be made with different independent variables and each time the AIC will be calculated. The model with the lowest AIC will be the final model.

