Participants will fill in the IBS-SSS and obtain a score between 0 and 500. The difference in score before and after the fertility treatment will be calculated. This score difference, which is a continuous outcome, will be used in a multiple linear regression model. This model estimates how several independent variables influence a single outcome. The regression analysis will show which independent variables (such as ethnicity, anxiety scores, duration of the desire to have children,...) have an influence on the score difference of IBS-SSS questionnaire. AIC will be used to evaluate the different possible models which will include different independent variables. The model with the lowest AIC will be used.

All analyses will be performed with SPSS.

11 Ethical Considerations

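### Lowest-AIC selection does not suit H3 to H11, which are worded as significance claims, and the logistic model has few expected IBS cases for its predictors

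*Protocol*

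**What the plan says.** Section 10.5 models meeting the IBS criteria (yes/no) by logistic regression and states: "This regression model will be used for the PCOS group and the social freezing group". On predictors it says: "The independent variables include GAD-7 score, PHQ-9 score, ethnicity, duration of the desire to have children, the number of follicles found on the US", and the list then trails off, so it is open. Models with different predictors are compared by AIC, and "The model with the lowest AIC will be the final model". The change in IBS-SSS is analysed by multiple linear regression under the same rule: "The model with the lowest AIC will be used". The section sets no limit on candidates, no minimum number of cases, no penalisation and no allowance for the search.

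Section 6.2.1 words H3 to H11 as significant associations or differences. Section 6.3 separately plans before-and-after comparisons in subgroups by stimulation type, infertility duration, ethnicity, hormonal profile, ultrasound reaction and PCOS type. The endpoints in Section 4 add the number of earlier treatments.

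On size, Section 4 says "This study will be an explorative study with a PCOS group of 60 and social freezing group of 60" and that "there is not enough data to do a power analysis before starting this study". On prevalence, Section 5.6 gives 3.8% by Rome IV, 10.1% by Rome III and a doubled risk in PCOS. Section 5.9 gives a range of 7.9% to 49.3%.

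**The concern.** AIC ranks models by fit. It does not produce tests. A p-value read from the winning model is computed as if that model had been the only one considered. A factor that AIC drops gets no regression estimate or confidence interval, even when a hypothesis names it. The logistic model has a further difficulty: its information is set by the number of women with IBS, not by the number enrolled, and the protocol's own prevalences make that number small. The study could report factors as significant that reflect the search, or odds ratios that have no finite estimate.

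**Working it through.** **The plan's own figure.** The 120 is taken by analogy with a cited study of 124 participants. No event count, alpha or power is given, so there is nothing to reproduce. I assume a two-sided alpha of 0.05.

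**1. Cases per predictor in the logistic model.** Cases = 60 × rate. Cases per predictor = cases ÷ 5, for the five named predictors.

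| Rate | Source | Cases in 60 | Per predictor |
|---|---|---|---|
| 3.8% | Rome IV, Section 5.6 | 2.3 | 0.46 |
| 7.6% | Rome IV doubled for PCOS | 4.6 | 0.91 |
| 10.1% | Rome III, Section 5.6 | 6.1 | 1.2 |
| 20.2% | Rome III doubled for PCOS | 12.1 | 2.4 |
| 7.9% | lower rate, Section 5.9 | 4.7 | 0.95 |
| 49.3% | upper rate, Section 5.9 | 29.6 | 5.9 |

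At 3.8% the chance of no case at all in a group is (1 − 0.038)^60 = 0.098, and the chance of fewer than five is 0.92. Pooling both groups gives 2.28 + 4.56 = 6.8 cases by Rome IV and 6.06 + 12.12 = 18.2 by Rome III, or 1.4 and 3.6 per predictor. Pooling alone does not solve the problem.

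**2. Separation (no finite estimate), all five predictors in the model.** Simulation with n = 60 and 300 runs per cell. The predictor distributions are assumptions.

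| Predictors | 2 cases | 4 | 6 | 12 |
|---|---|---|---|---|
| Five continuous | 18% | 2% | 0% | 0% |
| One of the five binary (30%) | 62% | 22% | 14% | 2% |
| Ethnicity in three levels (70/20/10%) | 100% | 84% | 66% | 34% |

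The spread comes from how ethnicity is coded, which the protocol does not say. The plan would report the AIC-chosen model, not the full one. With three-level ethnicity, the chosen model was separated in 33%, 16%, 17% and 12% of data sets at rates of 3.8%, 7.6%, 10.1% and 20.2%.

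**3. False positives in the linear model.** AIC keeps a one-parameter noise term when its likelihood-ratio statistic exceeds 2, with probability P(χ²₁ > 2) = 0.157. For five independent candidates, the chance of keeping at least one is 1 − (1 − 0.157)^5 = 0.575 (simulated: 60 to 61%). A kept noise term has p < 0.05 about 0.05 ÷ 0.157 = 32% of the time.

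The comparator is the same number of tests without selection: 1 − 0.95^5 = 22.6% and 1 − 0.95^8 = 33.7%. Null simulations at n = 60 gave:

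| Candidates | At least one p < 0.05 after AIC | Full model, no selection | Paired difference |
|---|---|---|---|
| 5 | 24 to 27% | 21 to 22% | 24 − 22 = 2; 24 − 21 = 3 |
| 8 | 36 to 39% | 30 to 33% | 36 − 30 = 6; 39 − 33 = 6 |

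The differences use only runs in which both procedures were applied.

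**4. Which hypotheses lose their estimate.** The named candidates match H3 (PHQ-9), H4 (GAD-7), H7 (duration), H8 (ethnicity) and H11 (follicles). If AIC drops the factor for H7, H8 or H11, the subgroup comparison in Section 6.3 remains. For H3 and H4 no other analysis of the association with IBS symptoms is described.

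**The case against.** **It is explorative.** The study is labelled so, is non-interventional, and the before-and-after comparisons for H1 and H2 are set out in Section 6.3 without reference to AIC. This stands and lowers the severity. It would fully excuse AIC used to generate hypotheses. It does not excuse using AIC to settle hypotheses worded as significant.

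**AIC is not the main culprit.** This also stands. A reader might infer from a 24 to 39% false-positive rate that selection causes it, or that the secondary results would be mostly noise. The comparison without selection shows most of it is multiplicity. All runs assumed no true effect, whereas Section 5.5 reports up to a threefold higher risk of anxiety or depression in IBS.

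**Dropped factors are not lost.** A reader might infer that every hypothesis in H3 to H11 could end with no result. Section 6.3 keeps comparisons for H5 and H7 to H11, and Section 4 has one for H6. The loss bites mainly on H3 and H4.

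**The prevalences may be too low.** Section 5.6 says women have up to three times the rate of men. With equal numbers of each sex, a threefold ratio makes the female rate 1.5 times the overall rate. The Rome III figure for PCOS then becomes 60 × 0.101 × 1.5 × 2 = 18.2 cases, or 3.6 per predictor. Even 49.3% gives under six. Cases remain few, but 2 to 12 is not the full range the protocol allows.

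**Per-group fitting is an inference.** The logistic text names both groups without saying that they are modelled separately, and the linear text mentions no split. The documents therefore do not support a claim that the linear analysis discards half its data.

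**Conclusion.** The point holds at moderate severity and should be fixed. The lowest-AIC rule is written into Section 10.5 and does not fit hypotheses worded as significant. With no true effect at n = 60, a false p < 0.05 appears in about 24 to 27% of data sets with five candidates and 36 to 39% with eight. About 3 and 6 points of that come from AIC and the rest from untreated multiplicity. The open list means the real number of candidates is unknown.

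The logistic model, if fitted per group, has about 2 to 12 cases on the Section 5.6 rates and about 30 at most on the Section 5.9 range. Separation is likely at the lower rates, but the documents support no single frequency because the coding of ethnicity is not given. Case counts and separation concern the logistic model only; the linear model will converge.

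The figures assume alpha 0.05, independent predictors, and rates from Sections 5.6 and 5.9 that apply to these women.

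**What to change.** Reword Section 10.5 as follows.

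- **H3 to H11:** replace the AIC rule with one fixed linear model per hypothesis. The outcome is IBS-SSS change; the terms are baseline IBS-SSS, group and the named factor. For H3 and H4 the factor is the change in PHQ-9 or GAD-7, as those hypotheses state.
- **Population:** use both groups where the factor applies to both. For H9 use PCOS women only, without the group term. Restrict H7 to women for whom infertility duration is defined.
- **H5 and H6:** treat as descriptive unless the factor varies under the entry criteria, since all women receive PPOS and must be in a first cycle or first stimulation.
- **Reporting:** give every estimate with its 95% CI whatever its significance, with Holm or FDR adjustment across the hypotheses actually tested (seven if H5 and H6 are descriptive: 9 − 2).
- **Rome-based logistic analysis:** limit it to one or two terms with Firth penalisation, labelled descriptive.
- **AIC models:** keep them, if wanted, as hypothesis-generating output without p-values.

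No visit or questionnaire changes. The costs are fewer mutually adjusted effects and a small software change: Firth estimation needs an SPSS extension or R, and if R is used the sentence assigning all analyses to SPSS must be amended.

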6.2.1 Secondary research hypotheses

H3.

Changes in depressive symptom levels are significantly associated with changes in IBS symptom severity in women undergoing fertility treatment.

H4.

Changes in anxiety levels are significantly associated with changes in IBS symptom severity in women undergoing fertility treatment.

H5.

Changes in IBS symptoms differ significantly according to the type of ovarian stimulation used during fertility treatment.

H6.

Changes in IBS symptoms differ significantly based on the number of fertility treatments received prior to the current treatment.

H7.

Changes in IBS symptoms differ significantly according to the duration of infertility.

H8.

The prevalence and/or change in IBS symptoms differ significantly across ethnic groups.

H9.

Among women with Polycystic Ovary Syndrome (PCOS), changes in IBS symptoms differ significantly according to PCOS phenotype.

H10.

Changes in IBS symptoms are significantly associated with the hormonal profile during controlled ovarian stimulation (COS).

H11.

Changes in IBS symptoms differ significantly according to the ovarian response assessed by ultrasound during COS.

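### H3 and H4 concern changes in depression and anxiety, but section 10.5 names no such change as a predictor and its lowest-AIC rule may drop either term, so neither hypothesis has a stated test

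*Protocol*

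**What the plan says.** Protocol section 6.2.1 states H3 as "Changes in depressive symptom levels are significantly associated with changes in IBS symptom severity in women undergoing fertility treatment" and H4 as "Changes in anxiety levels are significantly associated with changes in IBS symptom severity in women undergoing fertility treatment". In both, exposure and outcome are changes. Section 6.2 likewise lists changes in depression and in anxiety among the secondary objectives.

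Section 10.5 sets out two models:

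- **Linear model for severity.** For the IBS-SSS, "The difference in score before and after the fertility treatment will be calculated", and "This score difference, which is a continuous outcome, will be used in a multiple linear regression model". The predictors are an open list of "independent variables (such as ethnicity, anxiety scores, duration of the desire to have children", ending in an ellipsis.
- **Logistic model for IBS status.** "The independent variables include GAD-7 score, PHQ-9 score, ethnicity, duration of the desire to have children, the number of follicles found on the US", again ending in an ellipsis.

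For the linear model the selection rule is "The model with the lowest AIC will be used". No term is declared as always kept. Sections 9.2.2 and 9.2.3 have GAD-7, PHQ-9 and IBS-SSS completed both before stimulation and on the day of pick-up.

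**The concern.** The hypotheses and the analysis do not meet. A woman's anxiety level at one visit is a different exposure from how much her anxiety moved between visits. A level can be unrelated, or even oppositely related, to the IBS-SSS change when the two changes move together. The linear model, which is the one with IBS-SSS change as its outcome, names no depression measure at all. Even a term that enters the candidate set can be removed by AIC, which would leave H3 or H4 without an estimate in the final model.

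A related gap is that section 10.5 is silent on baseline IBS-SSS. When the outcome is a raw difference and a predictor correlates with the starting value, regression to the mean may be mistaken for a predictor effect. Section 5.5 reports more anxiety and depression in people with IBS, so such a correlation is plausible here.

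**Working it through.** The protocol gives no SD, correlation, effect size or power for this model, so there is no figure of its own to reproduce. The text can be compared directly; the arithmetic rests on assumptions.

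**1. Hypothesis against model**

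| | Exposure in 6.2.1 | Linear model in 10.5 | Logistic model in 10.5 |
|---|---|---|---|
| H3 | Change in depression | No depression measure named | PHQ-9 score, no time point |
| H4 | Change in anxiety | Anxiety scores, no time point | GAD-7 score, no time point |

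Neither row contains the hypothesised exposure in either model.

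**2. Cost of using a level instead of a change**

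Assumptions: true correlation c = 0.3 or 0.4 between GAD-7 change and IBS-SSS change; GAD-7 pre/post correlation ρ = 0.5 or 0.7 with equal variances; the score relates to IBS-SSS change only through GAD-7 change; two-sided 5%; n = 60 (one group) or 120 (both groups, from the target sample size).

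The correlation of a baseline score with its own change is (ρ − 1)/√(2(1 − ρ)) = −√((1 − ρ)/2), which is −0.50 at ρ = 0.5 and −0.387 at ρ = 0.7. For the post-treatment score the sign is positive. Multiplying by c gives the correlation that the score would show with IBS-SSS change. Power is Φ(atanh(r)·√(n − 3) − 1.96) plus a negligible second tail, where r is the correlation being tested.

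Example with c = 0.3 and n = 60: atanh(0.3)·√57 = 0.3095 × 7.550 = 2.337, and Φ(2.337 − 1.96) = 0.65.

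| c | ρ | Correlation using a score (size) | Power n = 60: change / score | Power n = 120: change / score |
|---|---|---|---|---|
| 0.3 | 0.5 | 0.150 | 0.65 / 0.21 | 0.92 / 0.37 |
| 0.3 | 0.7 | 0.116 | 0.65 / 0.14 | 0.92 / 0.24 |
| 0.4 | 0.5 | 0.200 | 0.89 / 0.33 | >0.99 / 0.59 |
| 0.4 | 0.7 | 0.155 | 0.89 / 0.22 | >0.99 / 0.39 |

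The sign is negative for a baseline score and positive for a post-treatment score, so the unstated time point decides the direction as well.

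**3. Baseline IBS-SSS: does adjustment help?**

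Simulation with 4,000 runs per scenario. IBS-SSS change was regressed on a baseline GAD-7 with no true effect. Assumed correlations: GAD-7 with baseline IBS-SSS 0.3 or 0.5; IBS-SSS pre/post 0.5 or 0.7.

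| How the data arise | False positives, no baseline term | False positives, baseline term added |
|---|---|---|
| Follow-up depends on the observed baseline only | 14-51% (n = 60), 25-79% (n = 120) | about 5% |
| Stable trait plus independent measurement error | about 5% | 17-74% (n = 60), 30-97% (n = 120) |

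In the first case the unadjusted slope is −0.09 to −0.25 SD per SD; in the second the adjusted slope is +0.10 to +0.33. Neither model is safe under both mechanisms.

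**The case against.** The strongest reply is that the covariate lists are open and illustrative. Baseline IBS-SSS is not excluded, and the term for anxiety scores could be read to include their change. A fuller list may sit in a statistical analysis plan that is not shown, and analysing a change score is not in itself an error. The study also calls itself exploratory, and H3 and H4 are secondary.

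Much of this stands. A reader might infer that the plan deliberately leaves out baseline IBS-SSS, or that it commits to anxiety and depression levels in the severity model. The text supports neither: it is silent on the first, and for the severity model it names anxiety only, with no time point.

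A reader might also infer that regression to the mean will distort the results and that baseline adjustment is the cure. That does not follow. The predictors are not randomised, and the simulation shows adjustment creating bias when baseline is an error-prone reading of a stable trait. Nor is the size robust. With a post-to-pre SD ratio k, IBS-SSS pre/post correlation r, and c now the predictor's correlation with baseline IBS-SSS, the spurious correlation is c(rk − 1)/√(1 + k² − 2rk). For c = 0.3-0.4 and k = 1 it is −0.12 to −0.20 over r = 0.5-0.7. At r = 0.7, k = 1.2, or r = 0.5, k = 1.5, it is only about −0.06 to −0.08.

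What the reply does not answer is the mismatch inside the protocol. Section 6.2.1 states two hypotheses about changes, section 10.5 describes the models meant to address them, and the selection rule there can remove the relevant term.

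**Conclusion.** The point holds for H3 and H4. Section 10.5 names no change in PHQ-9 or GAD-7, gives no time point for the scores it does name, mentions PHQ-9 only for the logistic model, and lets AIC discard any term. Followed as written, it can test a different exposure or return no estimate. That conclusion comes from the text alone. The size depends on the assumed correlations: power of 0.14-0.33 instead of 0.65-0.89 with 60 women, and 0.24-0.59 instead of 0.92 to above 0.99 with 120.

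On baseline IBS-SSS, only a limited conclusion is justified. Confusion with regression to the mean is possible, its direction and size depend on assumptions the protocol cannot settle, and the handling should be declared in advance. This is worth correcting, but it touches only secondary, exploratory hypotheses. The before/after comparison of IBS-SSS in H2 is unaffected.

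**What to change.** Add to section 10.5:

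1. For H3, regress IBS-SSS change on PHQ-9 change; for H4, in a separate model, on GAD-7 change. Define all changes as post minus pre. Prespecify both models, and keep the change term and group (PCOS or social freezing) whatever the AIC.
2. For any questionnaire score entered as a level, in the linear or the logistic model, state whether it is the before-treatment or the pick-up value.
3. Report the H3 and H4 models with and without baseline IBS-SSS. Declare beforehand, with a reason, which is the main analysis and which the sensitivity analysis, and note that adjustment can itself bias if baseline is measured with error.

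The cost is a few sentences. All the values are already collected at both visits, so there is no extra burden on participants and no change to the sample size. AIC selection can remain for the exploratory search among the other factors.

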5.5 IBS and psychosocial factors

Patients with IBS have a higher risk of suffering from anxiety or depression, up to threefold higher than healthy subjects. (11) IBS symptoms exacerbate during stressful times. (12) A study investigated the stress levels during first and repeat IVF cycles and found higher stress levels in all IVF cycles. Women with lower stress levels had a higher pregnancy rate. Stress management can be beneficial for pregnancy rates and for IBS symptom severity. (13)

Studies about the relationship between depression and IBS are scarce and results are often inconsistent. Most studies find a higher rate of depression in IBS patients. The impact of depression on IBS symptom severity and prevalence hasn't been fully explored. Depression and IBS share a similar pathogenesis which makes it difficult to study these two diseases separately. Both IBS and depression show a dysfunction of the neuroendocrine systems and the immune system. (14)

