8.2 Inclusion & exclusion criteria

Inclusion criteria **PCOS** group :

- Diagnosis of PCOS according to the 2004 Rotterdam criteria
- Initiating their first cycle of IVF treatment (PPOS and freeze only protocol)
- Nulliparous
- ≥ 18 years
- Willing to participate in the study
- Understanding Dutch, French or English

Exclusion criteria **PCOS** group :

- Known inflammatory bowel disorder
- Known major intestinal bowel disorder
- Known systemic or auto-immune disorder with implication for the GI system
- History of abdominal surgery (appendectomy and cholecystectomy allowed if >6 months earlier)
- History of gastro-enteritis in the past 6 weeks

Inclusion criteria **social freezing** group:

[figure not shown]
- Initiating their first ovarian stimulation protocol for elective oocyte cryopreservation (PPOS and freeze only protocol)
- Nulliparous
- ≥ 18 years
- Willing to participate in the study
- Understanding Dutch, French or English

Exclusion criteria **social freezing** group:

- Diagnosis of PCOS
- Known inflammatory bowel disorder
- Known major intestinal bowel disorder
- Known systemic or auto-immune disorder with implication for the GI system
- History of abdominal surgery (appendectomy and cholecystectomy allowed if >6 months earlier)
- History of gastro-enteritis in the past 6 weeks

9 Study Assessments and Procedures

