APPENDIX 2: IBS Symptom Severity Scale (IBS-SSS) (English version) (Rome Foundation)

1a. Do you currently (in the past 10 days) suffer from abdominal (stomach) pain?

No *Skip to question 3a*

Yes

1b. How severe was your abdominal (stomach) pain in the past 10 days? (Please indicate a number from 0 to 100, with 0 meaning “no pain” and 100 meaning “very severe pain”)

0 -- No pain

10

20

30

40

50

60

70

80

90

100 -- Very severe pain

2. Please enter the number of days you had the abdominal pain in the past 10 days. (For example, if you enter 4 it means that you had pain 4 out of 10 days. If you have pain every day, enter 10.)

0 days

1

2

3

4

5

6

7

8

9

10 days

3a. Do you currently (in the past 10 days) suffer from abdominal distention (bloating, swollen or tight stomach)?

Women: Please ignore distention related to your period when answering this question.

No *Skip to question 4*

Yes

3b. How severe was your abdominal distention/tightness in the past 10 days? (Please indicate a number from 0 to 100, with 0 meaning “no distention” and 100 meaning “very severe distention”)

0 -- No distention

10

20

30

40

50

60

70

80

90

100 -- Very severe distention

4. How dissatisfied are you with your bowel functioning in the past 10 days? (Please indicate a number from 0 to 100, with 0 meaning “Not dissatisfied” and 100 meaning “very dissatisfied”)

0 -- Not dissatisfied

10

20

30

40

50

60

70

80

90

100 -- Very dissatisfied

5. How much did abdominal pain or discomfort or altered bowel functioning affect or interfere with your life in general in the past 10 days? (Please indicate a number from 0 to 100, with 0 meaning “Not at all” and 100 meaning “completely”)

0 -- Not at all

10

20

30

40

50

60

70

80

90

100 -- Completely

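### The IBS-SSS change model (Protocol 10.5) uses ordinary linear regression on a score with a floor at 0; if zeros are common and GAD-7/PHQ-9 are right-skewed, standard errors for those levels are likely too small

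*Protocol*

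**What the plan says.** Section 10.5 of the Protocol describes the outcome thus: "Participants will fill in the IBS-SSS and obtain a score between 0 and 500". The change between visits is then modelled: "This score difference, which is a continuous outcome, will be used in a multiple linear regression model". The regression is meant to show which factors influence the change, with examples "such as ethnicity, anxiety scores, duration of the desire to have children". The covariate set is chosen by information criterion: "The model with the lowest AIC will be used". The section names no type of standard error and no residual check.

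Three other places bear on how the score will be distributed:

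- Section 8.2 contains no IBS criterion for entry in either group.
- Appendix 2 opens with a filter question, "Do you currently (in the past 10 days) suffer from abdominal (stomach) pain". A woman who answers no goes past pain severity and days with pain. A second filter does the same for distention severity.
- Section 5.5 links symptoms to the psychological predictors: "Patients with IBS have a higher risk of suffering from anxiety or depression, up to threefold higher than healthy subjects".

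**The concern.** Ordinary regression standard errors assume that the outcome has the same spread at every value of the predictors. A floor can break this. Women with no symptoms score at or near 0 at both visits, so their differences cluster round 0. Women with symptoms can move both ways and their differences spread out. If anxious or depressed women are also the more symptomatic ones, as section 5.5 suggests, the spread of the difference grows along predictors the model is meant to assess.

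At stake are the intervals and p-values for anxiety and depression levels. If the standard errors are too small, a factor can be called influential when the mean change does not depend on it. Doubling the sample does not cure this.

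**Working it through.** **1. No planned figure to reproduce.** The target of 60 + 60 = 120 is set by analogy with an earlier study of 124 women. The protocol gives no SD, effect size, share of zero scores or GAD-7 distribution, so every size below is conditional.

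**2. How strong is the floor?** Section 9.3.1 scores five topics from 0 to 100. Taking skipped items as 0 (the protocol does not say), a woman without pain or distention can score at most 2 × 100 = 200 of 500, from the two items nobody skips. Section 5.6 cites a prevalence of 3.8% (Rome IV) or 10.1% (Rome III). Applied directly, that is 120 × 0.038 = 4.6 or 120 × 0.101 = 12.1 women. It is only a rough guide: section 5.6 also gives a doubled risk in PCOS, and not having IBS is not the same as scoring 0.

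**3. When does unequal variance make the standard error too small?** For one predictor x, with residual variance σᵢ² for woman i:

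- true Var(b) = Σ(xᵢ − x̄)²σᵢ² / [Σ(xᵢ − x̄)²]²
- the ordinary formula targets σ̄² / Σ(xᵢ − x̄)², where σ̄² is the average variance.

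The ordinary value is too small when σᵢ² is positively correlated with (xᵢ − x̄)², that is, when women far from the mean of x are also the more variable ones. A right-skewed x with variance rising in x does this, because the far points lie in the high-variance tail. With a symmetric x and variance rising roughly in a straight line, high-variance points on one side are balanced by low-variance points on the other, and the error largely cancels.

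**4. Simulation.** Assumed inputs: normal latent severity with SD 90, within-woman correlation 0.6, rounded to 10 and clipped to 0-500; GAD-7 on 0-21, right-skewed or symmetric; severity rising 0, 8 or 15 points per GAD-7 point; mean shift between visits 0, 40 or 80; 4,000 runs per row. Selected rows at n = 120:

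| GAD-7 | Slope | Shift | At zero, baseline | SD of difference, lowest to highest anxiety quarter | Ordinary SE / true | 95% coverage, ordinary | 95% coverage, HC3 |
|---|---|---|---|---|---|---|---|
| skewed | 0 | 0 | 52% | 51 to 51 | 1.00 | 95.0% | 95.3% |
| skewed | 8 | 0 | 53% | 43 to 62 | 0.84 | 90.3% | 94.9% |
| skewed | 8 | 40 | 53% | 50 to 67 | 0.87 | 91.4% | 94.5% |
| skewed | 8 | 80 | 53% | 60 to 72 | 0.94 | 93.6% | 94.8% |
| skewed | 15 | 0 | 71% | 22 to 58 | 0.65 | 79.8% | 93.4% |
| skewed | 8 | 40 | 29% | 64 to 75 | 0.93 | 93.3% | 94.4% |
| skewed | 8 | 40 | 6% | 77 to 80 | 1.00 | 95.1% | 95.0% |
| symmetric | 8 | 0 | 36% | 51 to 69 | 0.99 | 95.1% | 94.8% |
| symmetric | 15 | 0 | 43% | 38 to 72 | 1.00 | 94.5% | 94.5% |

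The columns agree with each other. A ratio of 0.84 puts the cut-off at 1.96 × 0.84 = 1.65 true standard errors, a two-sided error of about 10% (coverage 90.3%). A ratio of 0.65 gives 1.96 × 0.65 = 1.27, about 20% (coverage 79.8%). Over all scenarios at n = 60 and 120, HC3 coverage was 92.8% to 96.8%; ordinary coverage was 79.5% to 96.6%.

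**5. Type I error with a true slope of zero.** Separate runs at n = 60 and 120 with a right-skewed anxiety level gave ordinary rejection rates of about 6-9% with 24-44% zeros and 12-15% with 55-58% zeros, against 5-7% with HC3. With a symmetric score or few zeros, the ordinary rate was 4-6%.

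**6. The stated hypotheses.** H3 and H4 (section 6.2.1) concern changes in depression and anxiety. With change in anxiety as predictor and severity following only the stable anxiety level, the ordinary SE was 0.98-1.00 of the true value, with coverage of 94-96%; another run gave type I error of about 5-7%. With GAD-7 itself floored at both visits (assumed 31% at zero), the rate was 6.7-8.9% at n = 60 and 5.9-8.2% at n = 120, against 4.7-6.0% with HC3. For the overall mean change (H2), interval coverage was 94-96% throughout.

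**The case against.** The strongest objection is that section 10.5 states nothing false. It names a regression model, and the type of standard error is commonly left to the analysis plan, which is not shown. This has weight and is one reason the point is minor. It does not remove the point: 10.5 fixes the model and supports it only by calling the difference continuous, without regard to the floor and skip questions in the protocol's own appendix.

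A reader might infer more: that variance rising with anxiety proves the standard errors too small. The documents do not support this. They give no distributions, and step 3 shows that rising variance alone is not enough. Nor do they establish that most women will score 0. A zero total also needs zeros on bowel dissatisfaction and interference with life, which nobody skips. Section 5.8 expects cramping, bloating and pain during IVF cycles, and the second visit is on the day of pick-up. A larger shift between visits weakens the effect (coverage 90.3%, 91.4% and 93.6% for shifts of 0, 40 and 80). Section 5.5 reports a raised risk in IBS patients, not a correlation between scores. On the other side, GAD-7 and PHQ-9 have a floor at 0 and the women are not selected for anxiety or depression, so right skew is the more plausible shape.

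It is also fair to say that robust standard errors leave the AIC untouched, so the same factors would be retained. Reporting p-values after that selection is the larger source of overstated precision: with 6 to 8 null predictors and well-behaved errors, about 30-38% of simulated runs gave at least one p-value below 0.05. That is a separate problem; correcting it would leave this one in place.

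**Conclusion.** The concern holds conditionally and is minor. If many women score at or near zero, and GAD-7 and PHQ-9 levels are right-skewed and related to severity, ordinary standard errors for those levels are likely too small: type I error of about 6-9% with 24-44% zeros and 12-15% with 55-58% zeros, against 5-7% with HC3. These shares and shapes are assumptions.

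With few zeros, a symmetric predictor or a predictor unrelated to severity, there is no material problem. For H3 and H4, worded as changes, the effect is slight: about 5-7% in one run and up to about 9% in another that floored GAD-7 at both visits. It would be wrong to conclude that the primary severity question is compromised, since the mean change (H2) is unaffected, or that the linear model must be abandoned, since its coefficients can stay.

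**What to change.** Add to section 10.5 that confidence intervals and p-values from the IBS-SSS change model use HC3 heteroscedasticity-robust standard errors, or a bootstrap that resamples women. The coefficients, covariates and sample size stay as planned.

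The cost is one sentence and one software setting, with slightly wider intervals for some factors. SPSS is the only package named, so confirm that the procedure chosen offers one of the two options. The sentence should not be presented as dealing with p-values after AIC selection, which need their own remedy.
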